## 10. KEY DERIVED VARIABLES

### 10.1. Outcome at 18 months

Derivation algorithm for stage 1 and intermediate stage (Month 18)	Derivation algorithm for stage 2 (Month 18)
Patient is dead (any reason of death and any time between drug intake and M18) $\Rightarrow$ YES $\Rightarrow$ Failure (stop) $\Downarrow$ NO (patient alive) $\Downarrow$	Patient requires rescue medication for HAT at M18 or required it before (between drug intake and M18) $\Rightarrow$ YES $\Rightarrow$ (definitive) Failure (stop) $\Downarrow$ NO rescue medication so far $\Downarrow$
Evidence of trypanosomes in any body fluid between drug intake and M18 visit $\Rightarrow$ YES $\Rightarrow$ (definitive) Failure (stop) $\Downarrow$ NO observed trypanosomes $\Downarrow$	Patient Lost to follow-up at M18 (no survival information at M18 and later) $\Rightarrow$ YES $\Rightarrow$ Failure (Stop) $\Downarrow$ NO (the patient is not lost to follow-up) $\Downarrow$
Non-haemorrhagic lumbar puncture at M18 and WBC in CSF at M18 >20 cells $\Rightarrow$ YES $\Rightarrow$ Failure (stop) $\Downarrow$ NO (WBC in CSF at M18 $\leq$ 20 cells or no reliable data concerning WBC in CSF at M18) $\Downarrow$	Non-haemorrhagic lumbar puncture at M18 and WBC in CSF <math>\leq</math>20 cells $\Rightarrow$ YES $\Rightarrow$ Success (stop) $\Downarrow$ NO (haemorrhagic CSF sample or no lumbar puncture at M18 for any reason) $\Downarrow$
No lumbar puncture at M18 or no reliable count of WBC in CSF at M18 but reliable number of WBC in CSF reported later (M24 or other additional visit) $\Rightarrow$ YES $\Rightarrow$ WBC in CSF >20 $\Rightarrow$ Failure (Stop) $\Rightarrow$ YES $\Rightarrow$ WBC in CSF <math>\leq</math>20 $\Rightarrow$ Success (Stop) $\Downarrow$ NO (No lumbar puncture at M18 and no later reliable count of WBC in CSF) $\Downarrow$	Patient has clinical signs or symptoms at M18 evoking a failure $\Rightarrow$ YES $\Rightarrow$ Failure (stop) $\Downarrow$ NO (no clinical signs or symptoms evoking a relapse at M18) $\Downarrow$

## 10.2. Outcome at 12 months

Derivation algorithm for stage 1 and intermediate stage (Month 12)	Derivation algorithm for stage 2 (Month 12)
Patient is dead (any reason of death and any time between drug intake and M12) ⇒ YES ⇒ Failure (stop)	
↓ NO (patient alive) ↓	
Patient requires rescue medication for HAT at M12 or before ⇒ YES ⇒ Failure (stop)	
↓ NO rescue medication so far ↓	
Evidence of trypanosomes in any body fluid at M12 or between drug intake and M12 visit ⇒ YES ⇒ (definitive) Failure (stop)	
↓ NO observed trypanosomes so far ↓	
Patient Lost to follow-up at 12M (no survival information at M12 and later) ⇒ YES ⇒ Failure (Stop)	
↓ NO (the patient is not lost to follow-up)	
↓ Non-haemorrhagic lumbar puncture at M12 and WBC in CSF >20 cells ⇒ YES ⇒ Failure (stop)	↓ Non-haemorrhagic lumbar puncture at M12 and WBC in CSF at M12 ≥ 50 cells ⇒ YES ⇒ Failure (stop)
↓ NO (WBC in CSF at M12 ≤ 20 cells or no reliable count of WBC in CSF at M12) ↓	↓ NO (WBC in CSF at M12 < 50 cells or no reliable count of WBC in CSF at M12)
Non-haemorrhagic lumbar puncture at M12 and WBC in CSF at M12 ≤20 cells ⇒ YES ⇒ Success (Stop)	Non-haemorrhagic lumbar puncture at M12 and WBC in CSF at M12 ≤20 cells ⇒ YES ⇒ Success (Stop)
↓ NO (no reliable count of WBC in CSF at M12) ↓	↓ NO (no reliable count of WBC in CSF at M12)
↓ ↓	Non-haemorrhagic lumbar puncture at M12 with WBC in CSF <50 but >20 and increase of WBC in CSF with respect to M6 or sign and symptoms evoking a failure ⇒ YES ⇒ Failure (stop)
↓ ↓	↓ NO (patient did not meet at least one of the previous criteria at M12)
↓ ↓	Non-haemorrhagic lumbar puncture at M12 with WBC in CSF <50 but >20 cells and decrease of WBC in CSF with respect to M6 and no signs and symptoms evoking a failure (success at M18 if status is available) ⇒ YES ⇒ Success (stop)
↓ ↓	↓ NO (patient did not meet at least one of the previous criteria)

Derivation algorithm for stage 1 and intermediate stage (Month 12)	Derivation algorithm for stage 2 (Month 12)

↓
 
No lumbar puncture at M12 or no reliable count of WBC in CSF at M12 but reliable number of WBC in CSF reported later (M18 or other additional visit)
 
⇒ YES ⇒ WBC in CSF >20 ⇒ Failure (Stop)
 
⇒ YES ⇒ WBC in CSF ≤20 and no signs or symptoms evoking a relapse ⇒ Success (Stop)
 
↓
 
NO (no later reliable count of WBC in CSF)
 
↓
 
No reliable WBC count in CSF at M12 and later and Failure at M18 for any reason
 
⇒ YES ⇒ Failure at M12 (Stop)
 
↓
 
NO
 
↓
 
Patient refused all post-treatment lumbar punctures but was met at M24 or later with no signs and symptoms evoking a relapse (normal activity)
 
⇒ YES ⇒ Success at M12
 
↓
 
NO (Patient not met at M24 or later)
 
↓
 
Patient refused all post treatment lumbar punctures
 
⇒ YES ⇒ Failure (Stop)
	
↓
 
No lumbar puncture at M12 or no reliable count of WBC in CSF at M12 but reliable number of WBC in CSF reported later (M18 or other additional visit)
 
⇒ YES ⇒ WBC in CSF >20 ⇒ Failure (Stop)
 
⇒ YES ⇒ WBC in CSF ≤20 ⇒ Success (Stop)
 
↓
 
NO (no later reliable count of WBC in CSF)
 
↓
 
No WBC count in CSF at M12 and later and Failure at M18 for any reason
 
⇒ YES ⇒ Failure at M12 (Stop)
 
↓
 
NO
 
↓
 
No reliable count of WBC in CSF at M18 and M12 but WBC counts at M6 available and no sign and symptoms evoking relapse at M12 or M18
 
⇒ YES ⇒ WBC in CSF at M6 ≤20 cells
 
⇒ Success (stop)
 
↓
 
NO ⇒ WBC in CSF at M6 >20 cells ⇒ Failure (Stop)
 
↓
 
NO (no lumbar puncture at M6, M12 and M18)
 
↓
 
Patient refused all post-treatment lumbar punctures but was met at M24 or later with no signs and symptoms evoking a relapse (normal activity)
 
⇒ YES ⇒ Success at M12
 
↓
 
NO (Patient not met at M24 or later)
 
↓
 
Patient refused all post treatment lumbar punctures
 
⇒ YES ⇒ Failure (Stop)

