9.1. Sample Size Determination

The sample size determination is based on the primary analysis. The expected success rate is between 87% and 91% depending on the percentage of early-stage patients included in the sample. The success rate for patients with late-stage HAT should be slightly below the expected success rate of 89% in the pivotal study, DNDIHATFEX004, which has a restricted, more homogeneous population.

As concerns early-stage patients, a meta-analysis performed by Hümbelin (11), on a sample of 2524 patients treated with pentamidine and indexed in the databases of four non-governmental organisations showed a relapse rate (presence of trypanosomes or CSF WBC \geq 20/µL) of 5.63% in patients followed for 6 months or less (142/2524), 8.20% in patients followed for 12 months or less (207/2524) and 9.23% in patients followed for 18 months or less. The expected success rate for early-stage patients should be close to 92%.

A sample size of 174 patients provides a precision of \pm 5% in the estimate if the expected success rate is 87% and if a Wald confidence interval is used.

Because the confidence interval will be calculated with an exact method (Clopper-Pearson approach) the lower arm of the 95% CI will be longer than the upper arm. The precision for the lower arm will be close to 6% and that of the upper arm will be close to 4.5 % if we consider an expected success rate of 87%. The precision will be greater if the success rate is higher.

Confidential Page 47 of 83

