9.8. Handling of Missing Data and Patients Lost to Follow-up

The endpoints are based on the outcome at 18 months.

For patients who attended the 18-month visit, but who refused the lumbar puncture planned at the visit, the **primary imputation method** will consist in checking for signs or symptoms of HAT. If no signs or symptoms of HAT are present and trypanosomes are negative, and if the outcome was considered as favourable at the last available assessment, the patients will be considered as treatment successes.

If these criteria are not fulfilled, the patients will be considered as treatment failures. The outcome for patients who did not attend the 18-month visit or later will also be considered as a failure, except for patients who fled the region due to armed conflict or natural disaster.

For the analysis at 12 months, if the lumbar puncture at 12 months is missing, data from the last available assessment will be used:

• the outcome at 18 months will be used, if a lumbar puncture was performed at that visit.

Confidential Page 52 of 83

- if a lumbar puncture was performed at 6 months, but not at 18 months, the patient will be considered as a success if the CSF WBC was ≤ 5/µL and lower as compared to prior values, if no trypanosomes were detected and if no HATrelated symptoms were present at 12 months.
- if a lumbar puncture was performed at 6 months and at 18 months, the outcome at 18 months will prevail.

In situations other than those described above and if no lumbar puncture is available after the start of treatment, the patients will be considered as failures.

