### 7.2. Type I error

For all analyses, the type I error ( $\alpha$ ) is set to 0.05 two-sided.

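### With no reliable month 12 CSF count, SAP 10.2 can score month 12 Success on a later count, despite rescue or trypanosomes after the month 12 window

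*SAP*

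**What the plan says.** SAP 10.2 derives the month 12 outcome as an ordered list of checks. Near the top is "Patient requires rescue medication for HAT at M12 or before", which gives Failure and stops. A matching check for trypanosomes also ends at the month 12 visit. Further down comes the step for "No lumbar puncture at M12 or no reliable count of WBC in CSF at M12 but reliable number of WBC in CSF reported later", with month 18 or any additional visit allowed as the source. A count above 20 is Failure. A count of 20 or less is Success and stops; the stage 1/intermediate column also requires no signs or symptoms of relapse, while the stage 2 column requires nothing more. The step that carries a month 18 failure back to month 12 comes after this one and applies only when no later reliable count exists.

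Protocol 9.8 treats a missing month 12 puncture differently: "the outcome at 18 months will be used, if a lumbar puncture was performed at that visit". SAP 7.6 states that the handling in protocol 9.8 is built into the algorithms of section 10. SAP section 11 lists changes to adverse event counting, to interim analyses and to the algorithm for a puncture that was never scheduled, but nothing on this point.

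SAP 10.1 (month 18) has the same structure. Its rescue check reads "Patient requires rescue medication for HAT at M18 or required it before", and its later-count step reads "No lumbar puncture at M18 or no reliable count of WBC in CSF at M18 but reliable number of WBC in CSF reported later", with month 24 or another additional visit as the source.

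**The concern.** Success is defined as cure. A CSF count taken after another HAT treatment does not show cure by fexinidazole, and neither does a low count at a visit where trypanosomes are found. The checks stop at the landmark while the permitted evidence reaches past it, and nothing covers the interval between them.

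The result is also internally inconsistent. A patient rescued after the month 12 window with no later puncture is a month 12 Failure through the carry-back step. Give the same patient a clean count after rescue and the outcome becomes Success. In the stage 2 branch for counts between 20 and 50, the authors do require consistency with month 18 status when it is known; here they do not.

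The error can only raise the success rate, in a single-arm open-label study whose main result is that rate. The protocol puts 12 and 18 months together in the primary endpoint; the SAP makes 18 months primary and 12 months secondary.

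**Working it through.** **1. Tracing the steps.** Take a patient with no reliable month 12 count, a month 18 CSF count of 20 or less, and no signs or symptoms. SAP 7.5 sets the month 12 window at days 300 to 509 and the month 18 window at days 510 to 659, and places unscheduled visits in the matching window. In 10.1, I read the death, rescue, trypanosome and lost-to-follow-up checks as common to both stage columns, as in 10.2.

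| Event | Month 12 by SAP 10.2 | Month 18 by SAP 10.1 | Month 12 by protocol 9.8 |
|---|---|---|---|
| Rescue by day 509 | Failure (early check) | Failure | Failure |
| Rescue from day 510, before the month 18 puncture | Success | Failure | Failure |
| No rescue; stage 2 with trypanosomes at month 18 | Success | Failure | Failure |

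The second and third rows are the defect. The third also applies in stage 1/intermediate if there are no signs or symptoms, because the later-count step reads only the white cell count and those signs.

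For 10.1 to fail in the same way, the month 18 count must be missing or unreliable, rescue or trypanosomes must come after day 659, and a puncture must follow at a visit the protocol does not schedule.

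**2. The plan's own precision.** Inputs: two-sided error that "is set to 0.05 two-sided" (SAP 7.2). Protocol 9.1 states "The expected success rate is between 87% and 91% depending on the percentage of early-stage patients included in the sample", and says of precision "A sample size of 174 patients provides a precision of" 5 points at 87%.

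- n = z² × p(1 − p) / d² = 1.96² × 0.87 × 0.13 / 0.05² = 173.8, so 174. The plan's figure is reproduced.
- Clopper-Pearson arms at 87% of 174 are 5.9 points below and 4.6 above, matching the protocol's approximate 6 and 4.5.

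**3. Size per patient.** 1/174 = 0.57 points. Starting from a reported 151/174:

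| Patients reclassified | Rate | Exact 95% CI |
|---|---|---|
| 0 | 151/174 = 86.8% | 80.8 to 91.4 |
| 1 | 150/174 = 86.2% | 80.2 to 91.0 |
| 2 | 149/174 = 85.6% | 79.5 to 90.5 |

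**4. How many patients.** The documents give neither the number of missing month 12 counts nor a late-relapse rate for fexinidazole. The only late-relapse figure is for pentamidine in early-stage disease (protocol 9.1): 8.20% by 12 months and 9.23% by 18 months.

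- Relapses between 12 and 18 months: 9.23% − 8.20% = 1.03 points; 174 × 0.0103 = 1.79 patients.
- With 5% to 30% of month 12 counts missing (my assumption), and every such relapse ending in a later count of 20 or less: 1.79 × 0.05 = 0.09 to 1.79 × 0.30 = 0.54 patients, or 0.05 to 0.31 points.
- Ceiling, if every month 12 count were missing: 1.79 patients, or 1.03 points.

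Under this proxy the figures are on the high side. Relapses up to day 509 are caught by the early checks, and relapses with a count above 20 at the month 18 puncture are Failures anyway.

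**The case against.** The strongest reply is that the gap is a drafting slip with little reach. Much of that stands.

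- **Rescue checks exist.** A reader might infer that any count taken after rescue can be scored as Success. It cannot: rescue at or before the landmark is Failure in both algorithms before the later-count step is reached.
- **The windows absorb earlier events.** A reader might take trypanosomes and rescue at month 15 as the typical case. That is about day 450, inside the month 12 window, so under SAP 7.5 it is a month 12 Failure. The gap opens at day 510.
- **The month 18 endpoint.** A reader might infer that the SAP's primary endpoint is equally exposed. The wording has the same structure, but the route needs events after day 659 and an unscheduled puncture.
- **Numbers.** A reader might suppose that several patients are affected, say 3 to 5. The documents do not support this; it exceeds the ceiling of 1.8 from their only late-relapse figure.
- **Rescued patients may leave.** The SAP disposition template counts rescue for relapse as premature withdrawal, so punctures after rescue may be uncommon. Protocol 8.3 does not list rescue as a reason for withdrawal, so this is not decisive.

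Two further defences do not close the gap. SAP 8.11 lets the data review decide which unscheduled-visit data to use, but the month 18 puncture is a scheduled visit. SAP 7.6 says that protocol 9.8 is included in the algorithms, but the algorithm as written does not reproduce it.

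It could also be said that a patient who relapses at month 17 may truly have been clear at month 12. With a reliable month 12 count of 20 or less, Success would indeed be right. Without one, the plan infers month 12 status from later evidence, and a count taken after rescue is not evidence of it.

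**Conclusion.** The defect holds for SAP 10.2. Without a reliable month 12 count, a later count of 20 or less gives month 12 Success even when rescue was given or trypanosomes were found after day 509 and up to that puncture. This contradicts the month 18 outcome for the same patient and departs from protocol 9.8 without being declared.

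The expected effect is small: well under one patient, with a ceiling of about 1.8 patients or 1 point, against exact interval arms of about 6 and 4.5 points. That rests on the pentamidine early-stage figure as a proxy, on the assumed 5% to 30% of missing month 12 counts, and on missingness being unrelated to relapse. It matters because the bias has one direction and the correction is simple, not because it is likely to change the study's conclusion. It is worth correcting, but it is not a critical fault. For 10.1 it is a precaution.

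**What to change.** In the later-count step of SAP 10.2, accept a later CSF count only if no rescue treatment for HAT and no trypanosomes in any body fluid are recorded after drug intake, up to and including the visit of that puncture; otherwise classify the patient as Failure. Add the same condition to the later-count step of 10.1.

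An alternative for 10.2 is to place the carry-back of a month 18 failure before the later-count step and reword its condition so that it needs only a missing month 12 count. This is closer to protocol 9.8, but it does not cover events after month 18, so the first option is the more complete.

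State in 10.2 that the rescue and trypanosome checks follow the SAP 7.5 windows, and record the change in section 11. Because version 3.0 already contains a change made after database lock, list the patients without a reliable month 12 count who had rescue or trypanosomes after day 509. Report the month 12 rate under both rules if there are any, and say so if there are none.

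The cost is one condition in two steps, using data already collected: rescue has its own CRF section, and parasitology is recorded at every follow-up visit. The planned 174 patients do not change. The success rate may come out slightly lower.

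### For patients with no reliable CSF count at month 12 or later, SAP 10.2 carries unrelated deaths and losses after month 12 back as month-12 failures, contrary to Protocol 9.8

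*SAP*

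**What the plan says.** SAP 10.2 derives the month-12 outcome by a sequence of steps, with one column for stage 1 and intermediate stage and one for stage 2.

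- **Opening steps.** Death is a failure for "any reason of death and any time between drug intake and M12". Loss to follow-up is a failure if there is "no survival information at M12 and later".
- **Patients with a usable count.** "Non-haemorrhagic lumbar puncture at M12 and WBC in CSF at M12 ≤20 cells" is a success and stops. If the month-12 count is missing, a later one replaces it: "No lumbar puncture at M12 or no reliable count of WBC in CSF at M12 but reliable number of WBC in CSF reported later".
- **The carry-back step.** In stage 1 and intermediate stage, "No reliable WBC count in CSF at M12 and later and Failure at M18 for any reason" gives a month-12 failure. The stage 2 column reads "No WBC count in CSF at M12 and later and Failure at M18 for any reason".
- **The month-6 step.** Only stage 2 has one, and it comes after the carry-back step: "No reliable count of WBC in CSF at M18 and M12 but WBC counts at M6 available and no sign and symptoms" evoking relapse. A month-6 count of 20/µL or less is then a success.

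SAP 10.1 counts death from any cause up to month 18, and absence of survival information at month 18 and later, as month-18 failures.

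Protocol 9.8 treats a missing month-12 puncture differently. The month-18 outcome stands in only where the patient was punctured at month 18. Otherwise, "if a lumbar puncture was performed at 6 months, but not at 18 months, the patient will be considered as a success if" the CSF count is 5/µL or less and below earlier values, no trypanosomes were found, and there are no HAT symptoms at month 12. Every other situation is a failure. SAP 7.6 states that the algorithms include the Protocol 9.8 handling. SAP section 11 lists no departure from it.

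**The concern.** The opening steps of SAP 10.2 close the window for death and loss at month 12. The carry-back step reopens it to month 18 for patients who lack a reliable count from month 12 onwards. Take a patient who is alive, free of symptoms and negative for trypanosomes at month 12, has a favourable month-6 puncture but none at month 12, and dies in an accident in month 15. That patient becomes a month-12 failure. A patient with the same course and a month-12 count of 20/µL or less has already stopped as a success.

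The SAP thus uses the month-18 outcome exactly where Protocol 9.8 does not, namely when no month-18 puncture exists. In stage 2 it also pre-empts the SAP's own month-6 success step.

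At stake is the month-12 success rate. SAP 6.2.1 makes it a secondary endpoint, but Protocol 2.2.1 names months 12 and 18 together as primary. For unrelated deaths and losses, the step can only lower that rate.

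**Working it through.** **Inputs.** N = 174, expected success 87% and a Wald half-width of 5 points (Protocol 9.1); two-sided 5% error (SAP 7.2); step order from SAP 10.2; month-18 failure from SAP 10.1; missing-puncture rule from Protocol 9.8.

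**1. The plan's own figure.** n = z²p(1−p)/d² = 1.96² × 0.87 × 0.13 / 0.05² = 173.8, so 174 (half-width 4.997 points). The exact interval at 151/174 has arms of 5.95 and 4.65 points, in line with the protocol's figures of about 6 and 4.5. The design figures reproduce. The documents give no figure for the disputed step.

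**2. Tracing the algorithm.** Take a patient with contact at month 12 and no rescue treatment or trypanosomes by then, who is a month-18 failure only through unrelated death or loss after month 12.

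| CSF counts available | Stage | SAP 10.2 as written | SAP 10.2 without the step |
|---|---|---|---|
| Month 12: 4/µL | any | Success | Success |
| None at month 12; later reliable count 4/µL, no relapse signs | any | Success | Success |
| None at month 12 or later; month 6: 4/µL | 2 | **Failure** | **Success** |
| None at month 12 or later; month 6: 4/µL | 1/intermediate | **Failure** | **No outcome assigned** |
| None at month 12 or later; month 6: 30/µL | 2 | Failure | Failure |
| No post-treatment puncture | any | Failure | Failure |

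In the two bold rows, Protocol 9.8 gives success if 4/µL is below earlier values, no trypanosomes were found and there are no HAT symptoms at month 12. In the last two rows Protocol 9.8 also gives failure. The SAP's exception for patients who refused every puncture but were met at month 24 or later cannot apply here: these patients are dead or have no survival information at month 18 and later.

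The step therefore changes the result only for a favourable month-6 puncture with no later reliable count. The fourth row also shows that the stage 1/intermediate column has neither a month-6 branch nor a default.

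**3. Size.** Each reclassified patient moves the rate by 1/174 = 0.57 points. The number k is not in the documents, so this is an assumed range starting from 151/174:

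| k | Month-12 rate | Exact 95% CI |
|---|---|---|
| 0 | 86.8% | 80.8 to 91.4 |
| 1 | 86.2% | 80.2 to 91.0 |
| 3 | 85.1% | 78.9 to 90.0 |
| 5 | 83.9% | 77.6 to 89.0 |
| 9 | 81.6% | 75.0 to 87.1 |

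Matching the 5-point design precision would take 5/0.57 = 8.7, or about 9 patients.

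**4. Does the sensitivity analysis repair it?** SAP 8.7.1 applies the Evaluable set to month 12. That set (SAP section 5) drops clearly unrelated deaths. For the month-12 outcome it drops only patients lost at month 12, so later losses remain as failures.

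**The case against.** The best defence is that scoring an unverified month-12 status as failure is conservative, and that the protocol itself looks beyond month 12. Protocol 9.8 says its endpoints rest on the 18-month outcome, and lets month 18 prevail when punctures exist at both months 6 and 18. This part stands: one cannot argue that later data must never affect the month-12 result. But the protocol ties that use to a month-18 puncture and the SAP does not. Caution does not explain a departure that SAP 7.6 implicitly denies and section 11 omits.

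Stronger readings are tempting, and the documents do not support them:

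- **Every month-18 failure becomes a month-12 failure.** It does not. A reliable month-12 count of 20/µL or less has already ended in success. So has a later reliable count at that level, provided that in stage 1/intermediate there are no relapse signs.
- **Any normal month-6 CSF would be a success under the protocol.** It would not. The count must also have fallen: 3/µL at baseline and 3/µL at month 6 is a failure there too.
- **Moving away in month 15 is enough.** It is not. SAP 10.1 requires absence of survival information, and Protocol 6.7.2 allows visits elsewhere. Protocol 9.8 also exempts patients who fled conflict or disaster from month-18 failure, although SAP 10.1 does not repeat that exemption.
- **The loss is several points.** One could multiply an assumed share without counts by an assumed share dead or lost. Neither share is documented, and the two are linked, because a lost patient has no later count. Only the effect per patient is supportable.

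**Conclusion.** The inconsistency is real and narrow. For patients without a reliable CSF count at month 12 or later, SAP 10.2 converts unrelated deaths and losses after month 12 into month-12 failures. This goes against its own month-12 limits and against Protocol 9.8. It alters the outcome only where the month-6 puncture was favourable, by 0.57 points per patient, always downwards. The number of such patients is unknown. The month-18 rate, which is the SAP's primary endpoint, is unaffected.

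Assumptions: the steps are read from top to bottom; the death and loss steps of SAP 10.1 apply to both stage columns; and the mITT population has the planned 174 patients. SAP section 4 cites protocol version 2.0, whereas the protocol reviewed here is marked version 3.0. I assume that section 9.8 is the same in both.

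**What to change.** 1. In both columns of SAP 10.2, limit the carry-back step to month-18 failures due to trypanosomes, rescue treatment for HAT, signs or symptoms of relapse, or a death not clearly unrelated to HAT or the IMP. Unexplained deaths then still count.
2. Classify patients lost after the month-12 contact, or who died after month 12 of clearly unrelated causes, by the Protocol 9.8 month-6 rule on data up to month 12. If that rule is not met, the outcome is failure.
3. Add a month-6 branch and a default to the stage 1/intermediate column.
4. Reconcile the stage 2 month-6 cut-off, which is 20/µL or less in the SAP but 5/µL or less and falling in the protocol. A count of 12/µL passes one and fails the other.
5. State which rule governs stage 2 patients who refused every post-treatment puncture. With the step narrowed, they could reach the SAP's month-24 success branch, whereas Protocol 9.8 makes them failures.
6. List the change in SAP section 11 and report the month-12 rate under both rules.

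The cost is a few algorithm lines and a re-run, with no new data. The real price is one more disclosed change after database lock, since section 11 already records one. Narrowing the step can only raise the month-12 rate, which is why both rates should be shown.

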12 months	12 months ± 4 weeks	Patient alive with no evidence of trypanosomes in any body fluid and CSF WBC ≤ 20/µL CSF WBS between 20 and 50/µL, and lower as compared to prior value(s)	Investigator to request an additional follow-up visit CSF WBC > 20/µL and non-significant increase from a clinical standpoint in relation to prior value(s) Any reason prompting the Investigator to request an additional	 CSF WBC > 20/µL and significant increase from a clinical standpoint in relation to prior value(s) Neurological signs or symptoms leading to use of 	Evidence of trypanosome s in any body fluid
18 months	18 months ± 4 weeks	Patient alive with no evidence of trypanosomes in any body fluid and CSF WBC ≤ 20/μL Patient with no signs of HAT and who refuses to undergo lumbar puncture and who, in the opinion of the Investigator does not require rescue treatment or an additional follow-up visit	follow-up visit • Any reason prompting the Investigator to request an additional follow-up visit	rescue treatment CSF WBC > 20/µL Neurological signs or symptoms leading to use of rescue treatment	Evidence of trypanosome s in any body fluid

6. Schedule of Study Procedures and Assessments

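### The SAP's month-12 algorithm leaves some patients without an outcome and departs from protocol 9.8, chiefly for stage 2 patients with only a month-6 count

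*SAP*

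**What the plan says.** M6, M12, M18 and M24 denote visits, and count means CSF white cells per µL.

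- **SAP 10.2, stage 2, M12 count 21–49.** Failure needs the count in that range "and increase of WBC in CSF with respect to M6 or sign and symptoms evoking a failure". Success needs "decrease of WBC in CSF with respect to M6 and no signs and symptoms evoking a failure (success at M18 if status is available", with the bracket left unexplained. Both steps compare with M6 only. Protocol Table 1 (12 months, favourable outcome) asks for a count in the 20–50 range "and lower as compared to prior value(s", which is a wider comparator.
- **SAP 10.2, stage 2, M6 count only.** The step "No reliable count of WBC in CSF at M18 and M12 but WBC counts at M6 available and no sign and symptoms evoking relapse", where the signs meant are those at the 12- or 18-month visit, gives Success when "WBC in CSF at M6 ≤20 cells", otherwise Failure.
- **SAP 10.2, stage 1/intermediate.** With no M12 count and a later count, Success needs "WBC in CSF ≤20 and no signs or symptoms evoking a relapse". There is no step for an M6 count alone.
- **SAP 10.2, both columns.** A patient who refused every post-treatment puncture but was met without signs at M24 or later is a Success. The last step makes the remaining refusers failures. It has no NO branch. SAP 10.1 (M18), in contrast, ends by counting all remaining cases as failures.
- **Protocol 9.8, M12 puncture missing.** "the outcome at 18 months will be used, if a lumbar puncture was performed at that visit". With an M6 puncture but none at M18, success needs a count of at most 5, lower than before, no trypanosomes, and no symptoms at 12 months. Other situations, and patients with no post-treatment puncture, are failures.
- **SAP 7.6** says the 9.8 handling is contained in the algorithms. **SAP 11** (changes from the protocol) mentions none of the differences above.

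**The concern.** A derivation algorithm has to give every patient one result. Where it does not, two analysts can report different 12-month rates from the same data. The unclassified patients could fall into the Missing row of the success-rate template (SAP 9.2.8), for which no denominator rule is given, or they could be assigned once the data are visible. The study is open-label, and SAP 11 already records an algorithm change after database lock. Where 10.2 does give a result that differs from 9.8, the reader is told the opposite, namely that 9.8 has been implemented.

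**Working it through.** **1. Scale, from the plan's own figure.** Protocol 9.1: p = 0.87, half-width d = 0.05. n = 1.96² × 0.87 × 0.13 / 0.05² = 173.8, so 174 as stated. The exact interval at 151/174 has arms of 5.95 and 4.65 points, against the protocol's approximate 6 and 4.5. One patient is worth 1/174 = 0.57 points.

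**2. Firm gap (stage 2, M12 count 30, no signs, M6 missing or also 30).** The count is not ≥50 and not ≤20. There is no increase from M6 and no sign, so the failure step does not apply. There is no decrease, so the success step does not apply. Every later step requires that M12 has no usable count or that all punctures were refused. The patient leaves the column with no result. The 12-month rules of 9.8 open with a missing M12 puncture, so they do not reach this patient.

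**3. Conditional gap.** If the bracket about M18 success is a condition, a stage 2 patient with a falling M12 count of 21–49, no signs and M18 Failure is also undefined. If it is only a comment, the patient is a Success.

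**4. Gaps in 10.2 that 9.8 would resolve.**

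- Stage 1/intermediate, M6 count only, no signs at M18. SAP 10.1 gives M18 Success if its page-broken cell is read with its continuation, so M18 Failure is not carried back. No later step of 10.2 fits.
- Stage 1/intermediate, no M12 count, later count ≤20, signs present, no rescue given. 10.2 has no step for this. Where the later count is at M18, 9.8 uses the M18 outcome. In 10.1 only patients on the branch "NO (haemorrhagic CSF sample or no lumbar puncture at M18 for any reason" go past the ≤20 step, so that outcome is Success.
- Stage 2, M6 count only (≤50), signs at M12 but none at M18, no rescue given. This reads the no-signs condition as none at either visit. 9.8 gives failure.

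**5. M6-only patients side by side** (no signs, no trypanosomes, no later count):

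| M6 count | Protocol 9.8 | 10.2 stage 2 | 10.2 stage 1/intermediate |
|---|---|---|---|
| ≤5, lower than before | success | Success | none |
| ≤5, not lower | failure | Success | none |
| 6–20 | failure | Success | none |
| 21 or more | failure | Failure | none |

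**6. No post-treatment puncture, met at M24 without signs.** In stage 1/intermediate, on the same reading of 10.1, 10.2 gives Success and 9.8 gives failure. In stage 2 the M24 step cannot be reached: 10.1 needs an M6 count for Success, so M18 is Failure and 10.2 carries it back.

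**7. Enumeration.** Counts at M6, M12 and M18 from {missing, 3, 15, 30, 40, 60}, signs yes/no at M12 and M18, and seen, lost or dead after M12, with no rescue, no trypanosomes and no count after M18:

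- Patterns per column: 6³ × 4 + 6² × 2 × 2 = 864 + 144 = 1008.
- Stage 2 with no M12 outcome: 28 (M6 missing) + 28 (M6 equal) + 4 (M6 only, signs at M12) = 60. This rises to 90 if the bracket is a condition and every M18 Failure counts as an available status.
- Stage 1/intermediate with no M12 outcome: 36 (M18 count ≤20 with signs at either visit) + 10 (M6 only) = 46.

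These are input patterns, not patient frequencies.

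**8. Size.** Assume 151 clear successes and k unclassified patients among 174. The documents do not give k.

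| k | as failures | left out | as successes |
|---|---|---|---|
| 1 | 86.8% | 151/173 = 87.3% | 152/174 = 87.4% |
| 3 | 86.8% | 151/171 = 88.3% | 154/174 = 88.5% |
| 5 | 86.8% | 151/169 = 89.3% | 156/174 = 89.7% |

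Exact 95% intervals: 151/174, 80.8–91.4; 151/169, 83.7–93.6; 156/174, 84.1–93.8.

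**The case against.** **Protocol 9.8 fills the gaps.** This is right for the three groups in step 4: the protocol has an answer that 10.2 fails to carry. It does not hold for step 2, since the residual sentence of 9.8 closes a list that begins with a missing M12 puncture.

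**Rescue treatment removes most patients with signs.** Protocol 5.6.5 provides rescue for patients showing signs of relapse, and rescue is an early Failure in both algorithms. If it is given, the 4 stage 2 patterns with signs at M12, and 24 of the 36 stage 1/intermediate patterns, are failures before any gap is reached. The other 12 (signs only at M18) still get nothing from 10.2, but M18 becomes Failure and so does M12 under 9.8. A reader might infer that a later count ≤20 with signs is always a success under 9.8. That holds only without rescue. Such patients are possible, because Table 1 ties probable relapse to neurological signs that led to rescue.

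**The M24 successes already have a sensitivity analysis.** SAP 5 excludes patients without a post-treatment puncture from the Evaluable set, and SAP 8.7.1 applies that analysis at 12 months. This is correct, but the main mITT analysis still counts them.

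**The page-broken cell in 10.1 might mean Failure.** Success is the likelier reading. If Failure were literal, the stage 1/intermediate M6-only gap and the M24 difference would disappear. The stage 2 gaps, the stage 2 M6 limit and the later-count gap would remain.

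**Exact ties are unlikely.** This is fair. The missing M6 count is the more plausible way into the firm gap.

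**M6 counts of 21–50 in stage 2.** These give M18 Success (10.1 allows ≤50) but M12 Failure, which a reader might call an error. It is not one in 10.2, since 9.8 also gives failure at 12 months.

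**Conclusion.** The point holds and should be fixed. The missing closing rule and the stage 2 gap for M12 counts of 21–49 are internal to the SAP and do not depend on the protocol version. The contradiction for stage 2 M6-only patients (counts of 6–20, or ≤5 without a fall) is clear against protocol 3.0. The SAP cites version 2.0, and SAP 11 describes a section 9.7 that differs from the one supplied, so whether 9.8 read the same in 2.0 cannot be checked. The stage 1/intermediate M6-only gap and the M24 difference rest on reading the broken cell as Success. The other two gaps that 9.8 resolves rest on no rescue having been given.

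Five unclassified patients, an assumed number, would open a range of 2.9 points (5/174) in the 12-month rate. Five patients covered by the contradictory rules would raise it against 9.8 by the same amount. A reader might infer that the primary result is biased. The documents do not support this: the SAP's primary endpoint is M18 and does not use 10.2. Nor is every effect towards success. The rules that contradict 9.8 are, but the gaps can go either way.

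**What to change.** In SAP 10.2:

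1. For stage 2 M12 counts of 21–49, state the comparator and the result when M6 is missing and when it is equal, reconciled with Table 1. Say whether the M18 bracket is a condition and, if so, whether an imputed M18 Failure is an available status.
2. Carry over the 9.8 rules for M6-only patients and for patients with an M18 puncture but none at M12. Give a stated result when the later count comes from another visit.
3. Only then end both columns by counting all remaining cases as failures. Added alone, that line would turn some 9.8 successes into failures: unrescued stage 1/intermediate patients with an M18 count ≤20 and signs, and stage 1/intermediate M6-only patients who meet the 9.8 criteria.
4. Reconcile the stage 2 M6-only limit and the M24 step with 9.8, or declare them in SAP 11 and show the M12 rate under both rules.
5. Cite the protocol version that applies, and report how many patients each new step resolves.

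The cost is SAP wording and a re-run of one derived variable. The 12-month rate may be slightly lower.
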